4.4 Drop-out (withdrawal) criteria

(1) Adverse events; (2) lack of efficacy; (3) trial protocol deviation (including poor compliance); (4) trial discontinuation is determined to be necessary for subjects by the investigator due to medical concerns; (5) the patients themselves request to withdraw the trial.

When a patient drops out, the investigators must fill in the reasons for dropout in the case report form, try their best to contact the patient, and complete as much of evaluation items and related examinations. The investigators should fill in the pathography in the last time the patient is contacted, including the patient's last medication time and efficacy. Those who drop out due to adverse events, whether investigational product-related or not, should be recorded in the case report form.

4.5 Criteria for trial discontinuation

Trial discontinuation means the clinical trial is not completed according to protocol and is prematurely discontinued. The main purpose of trial discontinuation is to protect the rights and interests of the subjects, ensure the quality of the trial, and avoid unnecessary economic losses.

- 1) If serious safety issues occur during the trial, the trial should be discontinued in time;
- 2) During the trial, major errors are found in the clinical trial protocol that make evaluation of drug

efficacy difficult; or major deviations from the well-designed protocol are found in the implementation that make evaluation of drug efficacy difficult if the trial is to be continued;

- 3) The sponsor requests to discontinue the trial (because of economic or management factors or others);
- 4) The administrative department in charge rescinds the trial.

5. Therapeutic Drug and Consolidation Radiotherapy Regimen

5.1 Investigational product

[figure not shown]
Protocol, short-course radiotherapy + neoadjuvant chemotherapy combined with immunotherapy (CAPOX + PD1 inhibitor)

5.2 Administration method

CAPOX: Oxaliplatin 130 mg/m² iv d1
Capecitabine 1000 mg/m² po bid, d1-14, q3w;

PD1 inhibitor camrelizumab: 200 mg iv drip, q3w;

5.3 Technical routes

5.4 Precautions

(1) Palpitation, chest tightness, dyspnea, cold limbs, and lowered blood pressure during chemotherapy should be observed closely, which indicate that the patient may have allergic reaction. Therefore, the treatment should be stopped immediately and the condition should be actively treated as allergic reaction.

(2) The dose-limiting toxicity of oxaliplatin is neurotoxicity, mainly in peripheral sensory nerves, manifested as sensory disturbance or/and paresthesia in the extremities. With or without algospasm, which is often cold-induced. These symptoms occur in 85-95% of patients receiving treatment. The symptoms usually decrease in treatment intervals, but gradually worsen with the increase of treatment cycles. Dysfunction includes an inability to perform fine movements, which is related to sensory disturbance. Evaluation with Levi sensory neurotoxicity classification criteria: 1) grade 0: no; 2) grade 1: paresthesia or dysesthesia (cold-induced), can be resolved within 1 week; 3) grade 2: paresthesia or dysesthesia, can be completely resolved within 21 days; 4) grade 3: paresthesia or dysesthesia, cannot be completely resolved within 21 days; 5) grade 4: paresthesia or dysesthesia, accompanied with dysfunction. The duration of the patient's symptoms and severity of pain and/or dysfunction are the indications for dose adjustment, and sometimes even treatment discontinuation is needed. When the treatment is discontinued, the neurological symptoms usually may improve.

(3) Camrelizumab is a PD-1 monoclonal antibody inhibitor and is an immune checkpoint inhibitor drug. PD-1 receptor inhibitors can block negative regulatory signals from T cells to relieve immunosuppression, which enhances the anti-tumor effect of T cells and may also abnormally enhance normal immune response, leading to immune tolerance imbalance. When PD-1 accumulates in normal tissues, the autoimmune-like inflammatory response appears, which is called immune-related adverse events (irAEs) and involves in multiple organs such as the skin, gastrointestinal tract, liver, endocrine, and lung. With reference to the clinical medication safety information in the package inserts of similar varieties nivolumab and pembrolizumab that have been listed abroad, camrelizumab may cause the following common adverse reactions: rash, pruritus, fatigue, weakness, fever, diarrhea, constipation, nausea, vomiting, decreased appetite, dyspnea, cough/productive cough, upper respiratory tract infection, musculoskeletal pain, joint pain, back pain, etc. In addition, camrelizumab is an antibody biomacromolecule. Vital signs, color of face and sweating of subjects should be closely monitored in clinical study, especially during the first administration, so as to detect signs of infusion reactions early. Combined with the results of preclinical animal experiments and clinical trials, camrelizumab has good safety and similar main drug-related adverse reactions to competitors. The investigator should closely monitor subjects for the above symptoms throughout the clinical trial, prepare appropriate medications and equipment, educate and encourage subjects to conduct self-monitoring. Possible common and severe adverse reactions caused by the investigational product camrelizumab should be closely monitored.

5.5 Concomitant medications

(1) During the clinical trial, except systemic intravenous chemotherapy according to the protocol, patients should stop using other drugs related to systemic treatment of tumor, including other chemotherapy drugs, targeted therapy, immunomodulators, Chinese patent medicine and other drugs that affect the efficacy;

(2) If there is a definite infection, or if the body temperature $\geq 38^{\circ}\text{C}$ and infectious fever cannot be excluded, antibiotics can be used and recorded in the CRF. The use of antifungal or antiviral drugs should also be recorded in the CRF.

(3) The subjects who receive concomitant medications that cause the difficulty of correct judgment of efficacy and safety should be treated as rejected subjects.

6. Medical Ethics Requirements

(1) The clinical trial protocol shall be approved by the ethics committee of the participating institution before it can be implemented. The approval document of the ethics committee on the clinical trial protocol will be copied to each clinical trial institution for the record.

(2) Informed consent form: The investigator should explain the objectives and process of the study to the enrolled subjects, and the informed consent form will be signed after obtaining the consent of the subjects.

This clinical trial will be conducted in accordance with the Declaration of Helsinki (2013 edition) and relevant Chinese Good Clinical Practice. The protocol should be reviewed and approved by the ethics committee of the hospital before the start of the trial. Any necessary modifications to the trial protocol during the clinical study should be reported to the ethics committee for the record.

7. Outcome Measures and Laboratory Tests

7.1 Medical history and physical examination:

Patients should be inquired by the doctor about their present and previous medical history in detail (including histories of allergy, cardiovascular disease, endocrine disease, respiratory system disease, and medication) before

being enrolled in the study. Systematic physical examinations and related laboratory tests will be performed before the trial and after the end of treatment. The medical history, physical examinations and laboratory tests results will be recorded in the CRF.

7.2 Laboratory Tests:

The enrolled patients will receive the following tests before treatment and after the end of the trial:

- 1) Blood routine test (HB + RBC + WBC), and coagulation function test;
- 2) Routine urine test (protein, RBC, WBC, and urine glucose), and stool routine;
- 3) Liver function (ALT and AST), renal function (BUN and Cr), electrolytes, and blood glucose;
- 4) Electrocardiogram, lung CT, liver MRI, abdominal and pelvic CT or MRI;
- 5) Blood tumor markers;
- 6) Urine pregnancy test in women of childbearing age (only before enrollment);
- 7) Thyroid function test.

All above tests on the subjects prior to treatment will be carried out in qualified laboratories certified by the clinical trial center, and the test results will be recorded in the CRF. Subjects with abnormality found in reexamination after the end of treatment should be followed up and reexamined, and the relation between the abnormality and the investigational product will be determined.

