4.1 Inclusion criteria

- 1) Age 18-75 years, male or female;
- 2) Rectal cancer diagnosed by histology, with initial treatment (untreated with surgery, radiotherapy, chemotherapy or targeted therapy);
- 3) Locally advanced rectal lesion: T3, T4a or 4b/N+;

- 4) With no severe hematologic disorder, cardiac, pulmonary, hepatic or renal dysfunction, or immunodeficiency;
- 5) Hemoglobin (Hb) ≥ 9 g/dL; white blood cell (WBC) $\geq 3 \times 10^9$ /L; neutrophil (ANC) $\geq 1.5 \times 10^9$ /L; platelet (Pt) $\geq 100 \times 10^9$ /L; bilirubin < 1.5 times the upper limit of normal value; aspartate aminotransferase (AST) & alanine aminotransferase (ALT) ≤ 2.5 times the upper limit of normal value; serum creatinine ≤ 1.5 times the upper limit of normal value or creatinine clearance rate ≥ 50 mL/min; thyroid stimulating hormone (TSH) \leq ULN (If abnormal, T3 and T4 levels should be referred to simultaneously. If T3 and T4 are normal, the patient can also be enrolled);
- 6) Males or females with reproductive ability who are willing to use contraception in the trial; ECOG performance status score is 0-1;
- 7) Patients or their family members agree to participate in the study and sign the informed consent form;
- 8) No other severe cardiopulmonary diseases.

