7.3 Observation of adverse events

(1) Clinical adverse events

All subjects should be observed for any adverse events that occur during the clinical trial. The clinical manifestations, severity, occurrence time, duration, treatment methods and prognostic measures of adverse events should be recorded in time, and the correlation between adverse events and the investigational product should be determined.

(2) Abnormal laboratory tests results

Subjects with abnormal results of the above tests after medication should be closely followed up and observed until they return to normal or stable, and the correlation between abnormality and the investigational product should be determined.

8. Efficacy Evaluation

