8.1 Safety evaluation

Changes in patients' subjective symptoms (nausea, vomiting, poor appetite, alopecia, etc.), KPS and PS scores before and after treatment; changes in indexes of blood routine, urine routine and stool routine tests, electrocardiogram, changes in physiological indexes (body temperature, blood pressure, heart rate, respiration) during medication, and comparison of hepatic and renal function before and after treatment.

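### Laboratory toxicity during the two treatment cycles is not systematically ascertained: section 7.2 fixes only a before and an after sample and does not name neutrophils, platelets or bilirubin, so its incidence may be underestimated

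*Protocol*

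**What the plan says.** All references are to the protocol.

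- **Test times.** Section 7.2 opens: "The enrolled patients will receive the following tests before treatment and after the end of the trial". Section 7.1 words the second time differently: "Systematic physical examinations and related laboratory tests will be performed before the trial and after the end of treatment". The paragraph closing 7.2 also speaks of re-examination once treatment has ended.
- **Analytes.** The blood item in 7.2 is "Blood routine test (HB + RBC + WBC), and coagulation function test" and the chemistry item is "Liver function (ALT and AST), renal function (BUN and Cr), electrolytes, and blood glucose". Thyroid function is on the list. Neutrophils, platelets and bilirubin are not named.
- **Eligibility.** Section 4.1 item 5 sets limits for neutrophils, for platelets and for bilirubin ("bilirubin < 1.5 times the upper limit of normal value").
- **Follow-up of abnormal results.** Section 7.3(2) says "Subjects with abnormal results of the above tests after medication should be closely followed up and observed until they return to normal or stable"; section 9.1(2) repeats this.
- **Safety evaluation.** Section 8.1 asks for "comparison of hepatic and renal function before and after treatment". A separate clause groups blood, urine and stool routine tests and the electrocardiogram with "changes in physiological indexes (body temperature, blood pressure, heart rate, respiration) during medication".
- **Laboratory summary.** Section 11.2 plans to describe shifts between normal and abnormal laboratory results from pre-treatment to post-treatment.
- **Adverse events.** Section 8.2 collects them from consent to 90 days after surgery and grades them by CTCAE 5.0.

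**The concern.** Safety is the stated secondary objective (section 2). The regimen combines chemotherapy with a checkpoint inhibitor, and section 5.4(3) itself lists the liver and the endocrine system among the organs that immune-related events affect. Such abnormalities can exist without symptoms, so finding them depends on when blood is taken and what is measured.

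A before-and-after pair shows only what is present at the second sample. A fall in counts or a rise in enzymes that occurs during the cycles and resolves has no planned measurement. Any such loss lowers the reported rate, which favours the regimen, and a 30-patient single-arm trial has no internal comparison that would reveal it.

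**Working it through.** **1. The passages side by side**

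| Question | Where | Answer |
|---|---|---|
| When is the second sample? | 7.2, opening | When the trial is over |
| | 7.1 and 7.2, close | When treatment is over |
| Any scheduled test within the cycles? | Available text | None found |
| Are neutrophils, platelets and bilirubin needed? | 4.1 item 5 | Yes, for eligibility |
| Are they named in the panel? | 7.2 | No |
| How are laboratory data summarised? | 11.2; 8.1 for liver and kidney | Before against after |

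The two versions of the second sample differ materially. The synopsis expects enrolment to finish in Oct. 2021 and the trial to end in Dec. 2025. Read literally, the opening of 7.2 could put the sample years after dosing.

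From first radiotherapy to surgery, the synopsis implies 1 week of radiotherapy + 1 week of rest + 2 × 3 weeks of cycles + 1 week = 9 weeks. If treatment in 7.1 means neoadjuvant treatment, the second sample can fall in the last of these weeks. The supportable statement is therefore that no test is scheduled during the cycles.

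**2. Do other sections fill the gap?**

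Sections 7.3(2) and 9.1(2) follow up abnormal results of the tests already listed. They add no sampling time and no analyte. Section 8.2 grades what is found, but a laboratory grade needs a value. Section 9.2 defines severity by the patient's complaint of discomfort, so a silent abnormality fits none of its categories.

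**3. Size, by illustration**

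The protocol gives no figure for laboratory toxicity, so there is none to reproduce. The only document input is the planned enrolment, 24 / (1 − 0.20) = 30. Two inputs are assumed:

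- p, the true share of patients with a relevant laboratory abnormality at any time during treatment: 10% to 30%.
- s, the share of those still abnormal at the final sample: 10% to 50%.

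Rate shown by the scheduled tests alone = p × s. Expected patients seen = 30 × p × s. Chance of seeing none = (1 − p × s)^30.

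| p | True expected of 30 | s | Rate shown | Expected seen of 30 | Chance of none |
|---|---|---|---|---|---|
| 10% | 3.0 | 10% | 1% | 0.3 | 0.74 |
| 10% | 3.0 | 50% | 5% | 1.5 | 0.215 |
| 20% | 6.0 | 10% | 2% | 0.6 | 0.545 |
| 20% | 6.0 | 50% | 10% | 3.0 | 0.042 |
| 30% | 9.0 | 10% | 3% | 0.9 | 0.401 |
| 30% | 9.0 | 50% | 15% | 4.5 | 0.008 |

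The rate shown runs from 1% to 15% against a true 10% to 30%. With s = 100% nothing is lost. For an analyte truly missing from the final panel, s = 0 as far as scheduled tests go, but that requires the bracketed list in 7.2 to be exhaustive.

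**The case against.** The strongest reply is that adverse events are observed in every patient throughout, are collected until 90 days after surgery, and are graded by CTCAE 5.0. Section 5.4(3) also asks for close watch for camrelizumab reactions. Symptomatic toxicity, and any abnormality found on an unscheduled test, would reach the record. This stands. A reader might infer that toxicity during treatment goes uncaptured and that the safety objective is bound to be answered too favourably; the protocol does not support that.

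Other replies also stand, in whole or in part:

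- A reader might infer that neutrophils, platelets and bilirubin are never measured. Eligibility cannot be decided without them, so they are measured at baseline, and the bracketed blood list may be a short form. What remains is that they are not named for the later sample.
- A reader might infer that the sections cannot all be followed. Section 7.2 does not forbid other tests, and the post-medication results in 7.3(2) can be those of the second sample. The plain textual conflict is over when that sample is taken; the rest are gaps and a list mismatch.
- The phrase in 8.1 about the medication period may cover blood routine tests as well as vital signs. If so, counts during dosing are intended, but no section says when they are taken. Hepatic and renal function stay before-and-after on either reading.
- The figure under 5.1 and any content under 5.3 were not available for this review. An assessment schedule there could close part of the gap.

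None of these replies supplies a defined set of on-treatment laboratory data or a summary that would use it.

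**Conclusion.** The point holds in limited form. On the available text, blood, liver and thyroid toxicity detectable only by laboratory test is not systematically ascertained during the two cycles, and its incidence may be underestimated. The direction is downward unless unscheduled tests fill the gap.

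The size is not known. The 1-15% range rests on assumed true rates and assumed persistence, and on counting scheduled tests alone; it illustrates the mechanism and does not forecast the trial's result. If sites test routinely around chemotherapy and record what they find, the loss could be small.

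The pCR endpoint is unaffected. The change is worth making because safety is the secondary objective and the remedy is cheap.

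**What to change.** 1. Reconcile 7.1, 7.2, 8.1, 11.2 and 4.1 item 5 on test times and analytes. State whether the second sample follows treatment or the trial, and which treatment is meant. Make clear whether the medication-period wording in 8.1 covers blood routine tests. The recorded panel should include the analytes that eligibility already requires.
2. Require every blood count, liver, renal and thyroid result obtained from first treatment to surgery to be entered in the CRF, whether or not it was scheduled.
3. Summarise laboratory safety by each patient's worst CTCAE 5.0 grade over that period, in addition to the before-and-after comparison.

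When to test patients during treatment is for the sponsor to set; no schedule is proposed here.

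The cost is protocol and CRF wording and a little more data entry per patient for at most 30 patients. Items 2 and 3 use results already obtained and require no additional blood sampling.

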7.3 Observation of adverse events

(1) Clinical adverse events

All subjects should be observed for any adverse events that occur during the clinical trial. The clinical manifestations, severity, occurrence time, duration, treatment methods and prognostic measures of adverse events should be recorded in time, and the correlation between adverse events and the investigational product should be determined.

(2) Abnormal laboratory tests results

Subjects with abnormal results of the above tests after medication should be closely followed up and observed until they return to normal or stable, and the correlation between abnormality and the investigational product should be determined.

8. Efficacy Evaluation

8.1 Safety evaluation

Changes in patients' subjective symptoms (nausea, vomiting, poor appetite, alopecia, etc.), KPS and PS scores before and after treatment; changes in indexes of blood routine, urine routine and stool routine tests, electrocardiogram, changes in physiological indexes (body temperature, blood pressure, heart rate, respiration) during medication, and comparison of hepatic and renal function before and after treatment.

8.2 Efficacy evaluation

Study endpoints

The primary endpoint was pathological complete response (pCR) rate, pCR was defined as the absence of viable tumour cells in the resected primary tumour specimen and all sampled regional lymph nodes (ypT0N0).

Secondary endpoints were 3-year event-free survival rate (defined as the percentage of patients without disease recurrence or progression or death due to any cause after 3-year follow-up), R0 resection rate (defined as the rate of negative margin microscopically), 3-year OS rate (defined as the percentage of patients alive after 3-year follow-up), complication rate, safety, and quality of life. Adverse events (AEs), duration of which collection was from the time the patient signed the informed consent form to 90 days after surgery, were graded according to the National Cancer Institute Common Terminology Criteria for Adverse Events, version 5.0.

Biomarker analysis

Tissue samples or paraffin sections must be provided as a patient was enrolled. Immunohistochemistry was performed to detect the expression of PD-L1 and DNA mis-match repair (MMR) proteins (MSH6, MSH2, MLH1 and PMS2). PD-L1 combined positive score (CPS) was evaluated using PD-L1 IHC 22C3 pharmDx (Agilent Technologies Inc., California, USA), defined as the number of PD-L1 positive cells (tumour cells, lymphocytes, macrophages) as a proportion of the total number of tumour cells multiplied by 100, Positive PD-L1 expression was considered when CPS was 1 or more. Comprehensive genomic profiling was conducted using targeted gene capture-based next-generation sequencing technology. Briefly, for formalin-fixed paraffin-embedded (FFPE) tissues, hematoxylin and eosin staining (H&E staining) was performed, and the stained sections were evaluated by a pathologist to ensure the tumor cells of $\geq 20\%$. DNA was extracted from the tumor tissues of patients using standard methods. A panel of 418 genes was captured and then sequenced through the Illumina NovaSeq6000 platform (Illumina, San Diego, USA) with 2×150 bp paired-end reads. The average of sequencing depth of tumor

tissues was $\geq 1000X$. Genomic alterations including tumor mutation burden (TMB), single nucleotide variants (SNV), short and long insertions and deletions (INDELs), copy number variants (CNV), and gene fusions were assessed.

Statistical analysis

According to the previous studies, the pCR rate after preoperative CRT in patients with LARC is approximately 15%. We expected that the regimen of SCRT combined with subsequent chemotherapy and camrelizumab could increase the pCR rate from 15% to 40%. A sample size of 24 patients was required to provide at least 80% power to detect this estimated improvement, in one-sided χ^2 -test with a significance level of 2.5%, and a 20% dropout was considered, resulting in that a total sample size of 30 patients was planned for this study.

Statistical analyses were conducted using SAS® software (version 9.2, SAS Institute Inc, Cary, USA). Continuous variables were summarized using medians and ranges, and categorical variables were described using the frequency and percentage. Baseline and safety analyses were performed for all enrolled patients (intention-to-treat [ITT] population), and efficacy analyses were conducted for those who administrated at least 1 dose of camrelizumab (full analysis set [FAS] population). P value of less than 0.05 was considered statistically significant.

The exploratory objective is: to evaluate the relation of biomarkers (e.g. PD-L1 and MSI) in tumor tissues and/or blood to PD1 efficacy and pCR. Biomarker detection will be carried out with the treated tissue and/or blood obtained prior to treatment.

Continuous variables that conform to normal distribution will be expressed as mean +/- standard deviation, minimum value and maximum value, and those do not conform to normal distribution will be expressed as median; categorical variables will be described in frequency and percentage, and 95% confidence interval will be calculated if necessary. Mean values between the two groups will be compared by t test, and the rates between the two groups will be compared by chi-square test. Survival analysis will be performed by the Kaplan-Meier method. Comparison between groups will be performed by bilateral log-rank test. All tests are two-sided, and 0.05 is taken as the level of the tests.

9. Adverse Event Monitoring

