Study objective:	To evaluate the efficacy and safety of preoperative short-course radiotherapy (SCRT) combined with subsequent chemotherapy (capecitabine and oxaliplatin) and PD1 inhibitor camrelizumab in patients with locally advanced rectal cancer (LARC).
Endpoints	
Primary endpoint: Pathological complete response (pCR) rate
 
Secondary endpoint: 3-year event-free survival rate R0 resection rate 3-year Overall survival rate Surgical complication rate Safety Quality of life

Sample size:	A total of 30 patients are planned to be enrolled in this study. The specific algorithm is as follows: this study will employ the single-arm design, with pCR rate as the primary endpoint. This study will adopt PASS 15 software, use tests for one proportion, and set $\alpha=0.025$ (one side) and $\text{power}=0.80$. The pCR rate of neoadjuvant therapy for locally advanced colorectal cancer was 15% previously, which is expected to reach 40% in this study. It is expected that 24 patients will need to be enrolled. Considering the drop-out rate of 20%, a total of 30 subjects should be enrolled
Study design	Patients with locally advanced rectal cancer (T3, T4a or 4b/N+) who are to receive preoperative neoadjuvant therapy: will receive preoperative local pelvic short-course radiotherapy. Radiotherapy will employ intensity-modulated radiation therapy, with a dose of 25 Gy/5 Fractions /1 week. One week later, a 3-week regimen of CAPOX chemotherapy combined with camrelizumab will be performed for 2 cycles. One week later, radical resection of rectal carcinoma will be performed. Postoperative adjuvant chemotherapy regimen will be determined by the doctor

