11.1 Data analysis set

Full analysis set (FAS): includes those who were administrated at least one dose of camrelizumab. When a primary efficacy indicator is missing, the previous result should be carried forward according to the principle of an intention to treat analysis. The missing values of comparability analysis and secondary efficacy indicators should not be subjected to data-carry-forward, and should be analyzed based on the actual data.

Per protocol set (PPS): includes subjects who meet the inclusion criteria, do not meet the exclusion criteria and have completed the treatment regimen, that is, those who meet the trial protocol, have good compliance and have filled all required sections of the CRF are included in the PPS analysis. In this trial, subjects who drop out after half of the treatment course due to aggravation should be included as invalid subjects in the PPS analysis.

Safety set (SS): subjects who have received at least one treatment and have actual safety assessment data. The missing safety data should not be subjected to data-carry-forward; some rejected subjects who are evaluable can be included, such as those with ages beyond the inclusion criteria, but excluding those who cannot be evaluated for safety due to the use of prohibited drugs. The number of subjects in the SS will be used as the denominator for the incidence of ARs.

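### The sample size takes the 20% drop-outs out of the denominator, but the efficacy set keeps any who received camrelizumab, so the stated 80% power is not assured

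*Protocol*

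**What the plan says.** The synopsis (Sample size) and section 8.2 (Statistical analysis) describe a single-arm comparison with a historical pCR rate. The regimen "could increase the pCR rate from 15% to 40"%, tested one-sided "with a significance level of 2.5"%. The synopsis gives the tool: "This study will adopt PASS 15 software, use tests for one proportion". Section 8.2 calls the test a one-sided χ² test and concludes: "A sample size of 24 patients was required to provide at least 80% power to detect this estimated improvement". The inflation follows in the synopsis, "Considering the drop-out rate of 20%, a total of 30 subjects should be enrolled", and again in section 8.2, "a 20% dropout was considered, resulting in that a total sample size of 30 patients was planned for this study".

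The efficacy population is defined differently. Section 8.2: "efficacy analyses were conducted for those who administrated at least 1 dose of camrelizumab (full analysis set [FAS] population". Section 11.1 repeats that the FAS "includes those who were administrated at least one dose of camrelizumab" and, for a missing primary endpoint, keeps the patient and carries the previous result forward. Section 8.2 defines pCR on the resected primary tumour and the sampled nodes. Section 4.3 separately removes enrolled subjects who have no evaluation records.

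**The concern.** Dividing 24 by 0.8 is right only when the six expected drop-outs disappear from the denominator and the remaining 24 carry the 40% rate. The FAS rule does that only for patients lost before their first camrelizumab dose. A patient who is dosed and never operated on stays in the denominator and has no earlier pCR result to carry forward, so in effect counts as a failure. The sample-size text makes no allowance for this and does not say which population the 40% refers to.

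The trial is judged on one threshold in about 30 patients. If power under its own analysis set is well below 80%, a negative result will be read as stronger evidence against the regimen than it is. The unclear denominator also leaves room to choose between dosed and evaluable patients once the results are known.

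**Working it through.** **Inputs.** Null rate 0.15, target 0.40, one-sided alpha 0.025, 24 patients needed, 20% drop-out, 30 enrolled (synopsis; section 8.2). FAS: at least one camrelizumab dose (sections 8.2, 11.1). Assumptions: exactly 6 of 30 drop out, none of them has a specimen, and the other 24 have a 40% pCR rate. The protocol does not say how many drop-outs come before the first dose, so this is varied from 0 to 6.

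**Cut-offs for a FAS of size n.**
- Exact: the smallest r with P(Bin(n, 0.15) ≥ r) ≤ 0.025.
- χ² (one-sample score test, no continuity correction): the smallest r with (r/n − 0.15)/√(0.15 × 0.85/n) ≥ 1.96.

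**Step 1: the protocol's figure.** At n = 24 both tests give r = 8, with true alpha 0.0199 and power P(Bin(24, 0.40) ≥ 8) = 0.808. With the exact test no n from 17 to 23 reaches 80%. The plain normal-approximation formula gives 20 (19.8 before rounding up), so 24 matches an exact calculation. 24/0.8 = 30. The stated figures are reproduced.

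**Step 2: all six dosed, none operated on.** FAS = 30; expected rate 0.40 × 24/30 = 0.32.
- Exact: r = 10 (true alpha 0.0097); power P(Bin(24, 0.40) ≥ 10) = 0.511.
- χ²: 0.15 + 1.96 × √(0.1275/30) = 0.278, and 0.278 × 30 = 8.3, so r = 9 (true alpha 0.0278); power P(Bin(24, 0.40) ≥ 9) = 0.672.
- Treating all 30 as Bin(30, 0.32) instead gives 0.506 and 0.659.

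**Step 3: other timings of the six drop-outs.**

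| Lost before dosing | FAS | Exact r | Exact power | χ² r | χ² power | χ² true alpha |
|---|---|---|---|---|---|---|
| 0 | 30 | 10 | 0.511 | 9 | 0.672 | 0.0278 |
| 1 | 29 | 9 | 0.672 | 9 | 0.672 | 0.0223 |
| 2 | 28 | 9 | 0.672 | 8 | 0.808 | 0.0486 |
| 3 | 27 | 9 | 0.672 | 8 | 0.808 | 0.0398 |
| 4 | 26 | 9 | 0.672 | 8 | 0.808 | 0.0321 |
| 5 | 25 | 9 | 0.672 | 8 | 0.808 | 0.0255 |
| 6 | 24 | 8 | 0.808 | 8 | 0.808 | 0.0199 |

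**Step 4: 40% as the rate over a full FAS of 30.** Exact: P(Bin(30, 0.40) ≥ 10) = 0.824. χ²: P(Bin(30, 0.40) ≥ 9) = 0.906.

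**Step 5: fewer dosed patients without a specimen, FAS still 30.** With rate 0.40 × (1 − d), power (exact / χ²) is 0.76 / 0.86 at d = 5%, 0.68 / 0.81 at 10%, 0.60 / 0.74 at 15% and 0.51 / 0.66 at 20%.

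**The case against.** The strongest reply is that the 40% carries no restriction to evaluable patients. Read as the FAS-wide rate, 30 patients give 82% or 91%, and the statement of at least 80% is true. That reading is open, so the arithmetic is not wrong in itself. It is hard to square with the drop-out inflation, though, because a rate that already absorbs dosed drop-outs would need inflation only for losses before dosing.

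Three further points have force.

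- A reader might infer that 80% power survives only if all six leave before dosing. That is true of the exact test only. With the χ² test that section 8.2 names, power stays at 81% for a FAS of 25 to 28. Those cut-offs, however, have true alpha from 0.0255 to 0.0486, so the power comes from exceeding the stated 2.5%.
- A reader might take 51% as the trial's power. The documents do not support that. It needs every drop-out to be dosed and none to be operated on, and the protocol gives no timing. Section 4.4 counts poor compliance and protocol deviation as drop-out, and such a patient may still have surgery and a pCR. Against this, only the radiotherapy week and one rest week precede the first dose, while two 3-week cycles and the further week before surgery follow it (2 weeks against 2 × 3 + 1 = 7), so assuming that every loss precedes dosing is not safe either.
- Counting missing cases as non-pCR is inferred from the pCR definition and the carry-forward rule; the protocol does not state it. The section 4.3 rule on missing evaluation records could remove some drop-outs, as the inflation assumes. This does not rescue the stated power. It shows that the document supports two different denominators.

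**Conclusion.** The point holds in conditional form. The sample size and the efficacy set use different denominators, and the stated 80% is not assured under the protocol's own drop-out rate. If 40% applies to operated patients and the six drop-outs have no specimen, power runs from 51% (exact, all six dosed) through 67% (exact with one to five dosed; χ² with five or six dosed) to 81% (all six lost before dosing, or χ² with one to four dosed at a true alpha above 2.5%). If 40% applies to a full FAS of 30, power is at or above the stated level. The result therefore rests on three things that the protocol leaves open: the population behind the 40%, how dosed patients without a specimen are counted, and whether the test is exact or χ². It is worth correcting before analysis, but it is not a fault in the calculation of 24 or 30.

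**What to change.** In the synopsis and section 8.2, with sections 4.3 and 11.1 brought into line:

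1. State that a patient given camrelizumab who has no resected specimen stays in the FAS and counts as non-pCR, and that removal for missing evaluation records (section 4.3) does not take such patients out.
2. Name the test. An exact binomial test keeps one-sided alpha at or below 2.5%; with 30 in the FAS its cut-off is 10 pCRs. If the χ² test is kept, the cut-off is 9 and the true alpha of 0.028 should be disclosed.
3. Restate power for the FAS. With 30 patients and the exact test it is 82% if 40% is the rate over the whole FAS, falling to about 51% if 20% of the FAS have no specimen and 40% of the rest have a pCR.

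The cost is a few sentences. No patients are added and the design is unchanged; the only downside is a less favourable stated power. Enlarging the trial is not asked for: at a FAS rate of 32% the exact test first reaches 80% power at 48 patients (0.811).
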